12.2.1 Analysis sets

Full Analysis Set (FAS)

The FAS consists of all randomized patients with at least one documented application of IMP and with at least one observed post-baseline value.

Per Protocol Set (PPS)

The PPS consists of all patients of the FAS without major protocol deviations. The evaluation of protocol deviations and whether they lead to the exclusion of a patient from the PPS will be performed during data review of the study.

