Boundary probability error of the first kind α	0,025
The probability of an error of the second kind β	0,2
The percentage point S.N.R. for α	1,96
The percentage point S.N.R. for β	0,84
The observed frequency of the positive effect for the control group $p_{control}$	0,75
Estimated value of the positive effect for the main group p_{main}	0,90
The value of the clinically important differences d	0,15
Estimated differences between groups e	0,0
The size of the main group n_{main}	97
The size of the control group $n_{control}$	97
Estimated share of departures	3
Adjusted main group size	100
Adjusted control group size	100

The final number of patients in each group was adjusted for their possible dropout. Thus, the final number of subjects in each group was 100 patients (200 patients in total).

Test treatment	
 - Treatment with Imupret® oral drops according to the respective Summary of Product characteristics (Imupret® coated tablets or oral drops during acute period for 5 days, afterwards switch to the subacute dosage regimen for further 28 days) - Sparing diet; fractional feeding (5-6 times a day) in small portions with the exception of coarse, spicy, heavily digestible foods - Elimination of factors irritating pharyngeal mucosa (thermal, chemical) 
 - As needed, Paracetamol (Acetaminifen) in a single dose of up to 400 mg not more than 3 times daily or paracetamol in a single dose of up to 500 mg 3-4 times daily (if necessary). - Topical agents such as Benzydamine, Lidocaine as needed (in case of severe sore throat). 	
Reference treatment	
 - Sparing diet; fractional feeding (5-6 times a day) in small portions with the exception of coarse, spicy, heavily digestible foods - Elimination of factors irritating pharyngeal mucosa (thermal, chemical) - As needed, Paracetamol (Acetaminifen) in a single dose of up to 400 mg not more than 3 times daily or paracetamol in a single dose of up to 500 mg 3-4 times daily (if necessary). - Topical agents such as Benzydamine, Lidocaine as needed (in case of severe sore throat). 	
Investigational Medicinal Product	Active (add on) treatment	Imupret® oral drops

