7 TRIAL OBJECTIVES

The aims of this clinical trial are:

To investigate the influence of Imupret prescriptions in the therapeutic concept of delayed prescription of antibiotics to:

- To compare the need for antibiotics in patients, received Imupret in addition to conventional therapy and in patients of the control group (received conventional therapy only)
- To evaluate the effect of the study drug in complex with conventional therapy versus conventional therapy only on regression of the tonsillitis symptoms
- To evaluate the effect of the study drug in complex with conventional therapy versus conventional therapy only on duration of antipyretic (paracetamol as antipyretic) administration.

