8.2 Sample size estimation

The clinical trial is designed in order to obtain a valid description of the in vivo performance of the active (add-on) treatment of Imupret in comparison to the reference standard treatment alone. Endpoints are defined as exploratory endpoints. Depending of the data finally obtained, several exploratory descriptive and statistic evaluations will be performed, so that a biometricaly based sample size estimation is not necessary. However, in order to guarantee a sufficient sample size for exploratory analyses of the data captured, a sample size of N=200 will be included. Treatments will be assorted in a 1:1 ratio, i.e. N=100 will receive an add-on treatment with Imupret® and N=100 will receive the standard treatment only.

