8.3 Trial treatment

The IMPs in this trial are Imupret® oral drops. The preparation is registered and available on the Ukrainian market without prescription. Therefore, the formulation, manufacturing, packaging and labelling of the IMPs follow the principles of Good Manufacturing Practice and currently valid national Ukrainian requirements. The detailed description covering all aspects regarding quality and safety of Imupret® oral drops are part of the respective Summary of Product characteristics.

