8.3.3 Reference treatment

All patients of the trial will undergo the reference treatment described below. However, only one of the two study groups (study group 1) will receive and add-on treatment with either Imupret® oral solution (see 0 and 8.3.2).

Reference treatment comprises instructions for patient's behavior as well as possible medical treatment when needed:

- Sparing diet with fractional feeding (5-6 times a day) in only small portions explicitly excluding coarse, spicy, or heavily digestible food
- At the discretion of the investigator, elimination of all factors irritating pharyngeal mucosa (e.g. thermal, chemical influence etc.)

At the discretion of the investigator, Paracetamol as single doses up to 500 mg – not more than 3-4 times daily

- At the discretion of the investigator, topical treatment like benzydamine, lidocaine (in case of severe sore throat)
- At the discretion of the investigator, antibiotic treatment in case it is indicated with e.g. amoxicillin clavulanate, cephalosporins (in case of prescription of antibiotics patients will be evaluated separately)

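### As written, the full analysis set requires intake of Imupret, so it and the per-protocol set contain no control patients, and no passage says which controls should qualify

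*Protocol*

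**What the plan says.** Protocol 12.2.1 defines the first analysis set: "The FAS consists of all randomized patients with at least one documented application of IMP and with at least one observed post-baseline value". The second is a subset of it: "The PPS consists of all patients of the FAS without major protocol deviations". The SAP, under Analysis sets, repeats both definitions and adds no rule by arm. No other efficacy set is defined.

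Section 8.3 says what the IMP is: "The IMPs in this trial are Imupret® oral drops". The synopsis agrees, listing the drops in the Investigational Medicinal Product row under "Active (add on) treatment". Section 10.9.2 also names the drops as the investigational product and deals with the reference treatment under its own sub-heading.

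Controls do not receive the drops. Section 8.2 says "N=100 will receive the standard treatment only", and 8.3.3 says that "only one of the two study groups (study group 1) will receive and add-on treatment". No placebo is described. The reference treatment consists of instructions on behaviour "as well as possible medical treatment when needed".

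Sections 12.2.2 and 12.2.3 then plan every efficacy result by treatment, including the number of patients in each arm who need an antibiotic.

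**The concern.** The entry condition is one that a control patient cannot meet. If a programmer applied it as it stands, the control column of every FAS and PPS table would be empty. Someone will notice and choose a different rule, but the documents do not say which.

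Two features make that open choice undesirable. Section 8.4 describes an open trial without blinding, so whoever settles the rule may know each child's arm and outcome. Section 12.1 has the analysis sets documented before hard lock, but 12.2 leaves the specifications of the evaluation until after the database is closed and allows inferential statistics to be data driven. Membership of an analysis set should not be open to choice at that stage, least of all for one arm only.

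**Working it through.** **Planned numbers.** The synopsis formula, with the entries in its Table 1, gives (1.96 + 0.84)² / (0.0 − 0.15)² × (0.75 × 0.25 + 0.90 × 0.10) = 7.84 / 0.0225 × 0.2775 = 96.7, rounded up to 97 per group. Allowing for departures, 97 + 3 = 100 (equally, 97 / 0.97 = 100). The stated 97 and 100 per group reproduce. (Sections 8.2 and 12.2 say that no formal sample size estimation applies; both routes arrive at 100 per arm.)

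**Literal application of the FAS rule.**

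| Condition | Imupret arm | Control arm |
|---|---|---|
| Randomised (8.2) | 100 | 100 |
| At least one documented application of Imupret drops (12.2.1 with 8.3) | up to 100 | 0 |
| At least one post-baseline value | up to 100 | 0 |
| PPS, a subset of the FAS | up to 100 | 0 |

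**Does other wording rescue the controls?** Several sections use IMP loosely. Section 9.4.1 asks for the last IMP intake of every withdrawn patient. Section 10.1 has IMP handed over after randomisation without separating the arms. An adverse-event example in 11.1.1 attaches the comparator to the IMP, and 11.1.3 refers to reference safety information for Imupret or the reference treatment. None of these redefines the IMP or says which controls enter an analysis set. In the other direction, 8.3 and 10.9.2 equate the IMP with Imupret, and 10.2 keeps IMP apart from antibiotics: a child given an antibiotic may be told to stop IMP.

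**Reading A, the most natural: the intake condition binds the Imupret arm only.** All controls with a post-baseline value qualify, and only Imupret non-starters are removed. Let p be the response among all patients randomised to Imupret and r the response among non-starters. The documents give no non-starter rate, so assume 3%. The response among starters is (p − 0.03r) / 0.97.

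- p = 75%, r = 100%: 72 / 0.97 = 74.2%, a shift of −0.8 points.
- p = 75%, r = 0: 75 / 0.97 = 77.3%, a shift of +2.3 points.
- p = 90%, r = 100%: 87 / 0.97 = 89.7%, a shift of −0.3 points.
- p = 90%, r = 0: 90 / 0.97 = 92.8%, a shift of +2.8 points.
- r = p: no shift.

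**Reading B, less likely: as-needed reference drugs count as IMP.** Controls who needed no drug are dropped, while Imupret patients qualify through Imupret whatever else they took. Let u be the share of controls who used any reference drug. Each dropped control has zero paracetamol days, so the mean among retained controls is the overall control mean divided by u. The direction is fixed: controls look worse on the antipyretic objective in section 7. The size is not, because the documents give no value of u. Purely as assumptions, u = 95%, 90% and 70% multiply the mean by 1.05, 1.11 and 1.43.

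The same division applies to the share taking antibiotics only if antibiotics are themselves reference drugs. Section 8.3.3 lists them there; the Reference treatment row of the synopsis does not.

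**The case against.** The strongest reply is that nobody would run a comparative trial with an empty control set. Sections 7, 8.2, 12.2.2 and 12.2.3 all compare two arms, the gap would be seen at the first table, and the obvious interpretation is nearly harmless. The trial also calls itself exploratory. Much of this stands. The intent is not in doubt, and Reading A probably matters little. But intent to include controls is not a rule for including them, and the SAP, where the rule belongs, repeats the sentence unchanged.

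A second reply is that the choice need not be made with knowledge of outcomes. Section 12.2 also says that technical details will be specified before analysis, and the abbreviation list contains a blind data review meeting. That meeting is not described anywhere else, and staff in an open trial may know the allocation. It is fair to say that the choice could be unblinded, not that it will be.

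A reader might also infer that the rule builds in a bias towards Imupret with a large excess of false positives. Under Reading B with antibiotics counted, no true difference and a two-sided 5% pooled z-test of 100 Imupret patients against 100u controls, exact enumeration gives 14.3% at u = 70% if 10% truly take antibiotics, and 33.3% if 25% do. The documents do not support that conclusion. Reading B rests on safety wording alone and sits badly with 8.3, 10.2 and 10.9.2. The drug-use and antibiotic rates are invented inputs. The synopsis omits antibiotics from the reference treatment, while 8.3.3 and 10.2 say that patients given them are evaluated separately. No test of the antibiotic share is specified. Reference-drug use in severe tonsillitis could well exceed 90%; at u = 95% the same calculation gives 5.2% and 5.7%, against 5.2% and 4.9% with nobody dropped.

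**Conclusion.** The definition is wrong as written and has to be corrected before analysis. On the plain text, both efficacy sets contain 0 of 100 controls, and the between-arm comparison for which the trial exists cannot be made on either. This conclusion rests on the documents' own identification of the IMP and needs no assumed rate.

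The practical consequence is narrower. The text leaves control membership undefined, to be settled in a trial where allocation may be known. Under the most natural reading the effect is small and of uncertain direction, between −0.8 and +2.8 points in the Imupret response at an assumed 3% of non-starters. The less likely reading would inflate paracetamol use among controls by an amount that the documents do not allow to be estimated, and would touch the antibiotic comparison only on a further assumption. It shows why the rule should be closed off; it is not a forecast of bias.

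**What to change.** In Protocol 12.2.1 and the SAP, replace the FAS sentence with: *FAS = all randomised patients, analysed in the arm to which they were randomised.* If a post-baseline value is still required, apply that condition identically in both arms and report exclusions per arm.

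The minimum acceptable repair is to state that the IMP-intake condition applies to the Imupret arm only and that all randomised controls qualify. That makes the set usable, but still removes non-starters from one arm alone.

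Wherever IMP is used in 9.4.1, 10.1, 11.1.1 and 11.1.3, align the term with 8.3 so that the wider reading cannot arise.

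The cost is one sentence in each document and a check of terminology, with no new data. The downside of the full fix is that Imupret patients who never start stay in their arm and slightly dilute the estimated effect.

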4 LIST OF ABBREVIATIONS AND DEFINITION OF TERMS

ADR	Adverse drug reaction
AE	Adverse Event
AR	Adverse reaction
BDRM	Blind Data Review Meeting
CRF	Case Report Form
CRO	Contract Research Organization
CTM	Clinical trial manager
ENT	Ear-nose-throat
EudraCT	European Union Drug Regulating Authorities Clinical Trials
FAS	Full analysis set
FPI	First Patient In
GCP	Good Clinical Practice
GMP	Good Manufacturing Practice
ICD	International Classification of Diseases
ICH	International Committee of Harmonization
IEC	Independent Ethics Committee
IMP	Investigational Medicinal Product
Int.	International
LPO	Last Patient Out
MedDRA	Medical Dictionary for Regulatory Activities
NSAID	Non-steroidal inflammatory drugs
PPS	Per protocol set
SAE	Serious Adverse Event
SAP	Statistical analysis plan
SE	Societas Europaea
SUSAR	Suspected Unexpected Serious Adverse Reaction
V	Visit
VAS	Visual analogue scale

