8.4 Randomization

The clinical part of the trial will be open and randomized with no blinding procedure. Subjects will be randomly assigned to one of the two possible treatments with according to the underlying randomization list. Randomization will be performed using [StatSoft – generator of random figures] software.

The appropriate number of the randomisation schedule and associated treatment will be allocated for each subject whose entry in the randomised part of the clinical trial is confirmed. The randomisation list will be part of the trial documentation.

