12 EVALUATIONS

12.1 Data Management

Data management comprises the following general processes in chronological order: Set-up of database, data entry and cleaning including query handling, coding procedures, data validation and final review of data.

Upon receipt of CRFs and respective raw data sheets, the data from the CRFs will be entered and transferred into the trial data base. Data base will be prepared for data entry and will reflect the final version of the CRF and raw data sheets. Adequate quality control methods will be applied. Identified discrepancies, will be queried by a responsible data manager using data clarification forms and forwarded to the investigator. Data sets and data base will be hard locked after all discrepancies are resolved and the analysis sets of subjects are documented. In case, that the data base has to be opened, this will be done only after agreement with all involved parties. All changes after data base hard lock will be tracked. All clinical data included in the data base will at least be listed.

For data coding (e.g. AEs, medical / surgical history, medication) internationally recognized and accepted dictionaries will be used (Medical Dictionary for Regulatory Activities (MedDRA) for AEs and WHO-dictionary for medication). In general, the latest version of medical dictionaries valid at data base setup will be used for coding throughout the clinical trial.

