12.2 Statistical evaluation

The statistical planning of the trial and the statistical analyses will be conducted following the principles specified in the ICH Topic E9 (ICH, 1998), and will be carried out by a qualified statistician in accordance with the ICH. Technical details of the statistical analyses will be specified prior to data analyses.

In general, there will be one main statistical evaluation.

Data base will be closed after all data are entered and cleaned.

In general, unless otherwise stated, continuous data will be summarized by means of descriptive statistics (mean, standard deviation (SD), median, quartiles, minimum, and maximum). Categorical variables will be described in contingency tables as absolute number and percentages.

AEs will be evaluated considering frequency and intensity. Furthermore, AEs will be evaluated considering relationship to the IMP, outcome, and seriousness. Both will be described by absolute and relative frequency. Descriptive statistics will be calculated for clinical laboratory parameters determined. Frequencies of values inside and out of normal range (i.e. above and below) will be given where possible.

This is an exploratory trial with no formal sample size estimation. Therefore, beneath descriptive statistics of efficacy endpoints, concluding statistics may be performed in a data driven way, in order to find clinically relevant differences between study participants, time points and treatments. Possible corrections to prevent an alpha inflation will be performed, if meaningful.

Specifications of the biometrical evaluation will be defined after all data management processes of the study phase will be terminated and data base was closed. In general, variables will be analyzed considering the underlying analysis set, treatment and time point, if meaningful.

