The FAS consists of all randomized patients with at least one documented application of IMP and with at least one observed post-baseline value.

Per Protocol Set (PPS)

The PPS consists of all patients of the FAS without major protocol deviations. The evaluation of protocol deviations and whether they lead to the exclusion of a patient from the PPS will be performed during data review of the study.

Primary endpoint

Main criterion for evaluation in the trial will be:

- Scores determined by the Local Tonsillitis Manifestations Scale refined by McIsaac's scale. Scores will be dichotomized to decide for two categories (therapy effective/therapy ineffective). Scores will be evaluated by treatment and time point, i.e. per visit
- Need for an antibacterial therapy, i.e. number of patients per treatment.

Secondary endpoints

- Scores/Intensity of each underlying disease symptom assessed by the Local Tonsillitis Manifestations Scale by treatment and time point, i.e. per visit
- Axillary temperature per treatment and measurement time point
- Patient's self-assessments on VAS per treatment and measurement time point
- Self-assessment of the symptoms by the patient.

Safety evaluation

AEs will be evaluated considering frequency and intensity. Furthermore, AEs will be evaluated considering relationship to the IMP, outcome, and seriousness. Both will be described by absolute and relative frequency. Descriptive statistics will be calculated for clinical laboratory parameters determined. Frequencies of values inside and out of normal range (i.e. above and below) will be given where possible.

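### Per-protocol membership is left to judgement at data review in an open trial, with no preset list of major deviations and no provision to mask arm or outcome

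*Protocol*

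**What the plan says.** - **Definition.** Protocol 12.2.1: "The PPS consists of all patients of the FAS without major protocol deviations". The word major is not defined, and no qualifying deviation is listed in the protocol or the SAP.
- **Who is excluded.** The same section leaves open "whether they lead to the exclusion of a patient from the PPS will be performed during data review of the study". The SAP, under Analysis sets, repeats that sentence and adds no criteria and no masking.
- **Blinding.** Protocol 8.4: "The clinical part of the trial will be open and randomized with no blinding procedure".
- **Masked review.** Protocol section 4 expands BDRM as "Blind Data Review Meeting". The abbreviation appears nowhere else in the protocol and nowhere in the SAP.
- **Timing.** Protocol 12.1: "Data sets and data base will be hard locked after all discrepancies are resolved and the analysis sets of subjects are documented". The same section says that changes after hard lock are tracked.
- **Analysis.** Protocol 12.2: "Specifications of the biometrical evaluation will be defined after all data management processes" have ended and the database is closed, and "concluding statistics may be performed in a data driven way". Neither the FAS nor the PPS is named as primary.

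**The concern.** A per-protocol set is only as credible as the independence of its exclusions from the result. Here the criteria are not fixed in advance, and nothing stated keeps arm and outcome away from the people who apply them. When the sets are documented, the data have been entered and cleaned, so both items exist in the database.

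The plan also gives a route by which exclusions could follow outcome without any intent. Only the Imupret arm takes drops 5-6 times daily, so only that arm can deviate on intake. Under 10.2, a child prescribed an antibiotic may be advised to stop the drops, and in the synopsis an indication for antibacterial therapy means that treatment was not effective. Such a child is both a treatment failure and a possible intake deviation. Removing such children from the Imupret arm, with no counterpart in the reference arm, would favour Imupret.

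At stake is how far a PPS result can be trusted. Because no set is primary, that result could be put forward as the main one.

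This is a separate matter from the late specification of statistical methods. It concerns who enters the denominator, and fixing the methods early would leave it open.

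**Working it through.** **Inputs.** From Table 1 of the synopsis: control rate 0.75, planned Imupret rate 0.90, z of 1.96 and 0.84, 97 per group, 100 per group after dropout. Assumed, because the documents give no deviation rate: the number of children excluded, and a pooled z test, since no PPS test is specified.

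**Plan's own figure.** (1.96 + 0.84)² / 0.15² × (0.75 × 0.25 + 0.90 × 0.10) = 7.84 / 0.0225 × 0.2775 = 96.69, rounded up to 97; 97 / 0.97 = 100. The group size reproduces. It serves here only as the denominator.

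**Error with no true effect.** Let a and b be the numbers of successes in the Imupret and reference arms, each binomial (100, 0.75). Remove k₁ failures from the Imupret arm and k₂ from the reference arm, so that n₁ = 100 − k₁ and n₂ = 100 − k₂. With p̄ = (a + b)/(n₁ + n₂),

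z = (a/n₁ − b/n₂) / √[p̄(1 − p̄)(1/n₁ + 1/n₂)].

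The error is the total probability of all pairs (a, b) with z ≥ 1.96, by exact enumeration.

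| Exclusions | Upper-tail error |
|---|---|
| None | 2.47% |
| 3 Imupret failures | 6.21% |
| 5 Imupret failures | 10.70% |
| 3 failures from each arm | 3.18% |
| 5 Imupret and 3 reference failures | 5.80% |
| Unrelated to outcome, 97 v 100 remain | 2.47% |
| Unrelated to outcome, 95 v 100 remain | 2.52% |

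At the expected count of 75 successes, dropping 3 failures shows 75/97 = 77.3% against 75%; dropping 5 shows 75/95 = 78.9%.

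**Effect on a single result.** Assumed observed results, 100 per arm, chi-square without correction:

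| Imupret v reference | p, no exclusions | Imupret failures dropped | p after |
|---|---|---|---|
| 85 v 75 | 0.077 | 2 | 0.036 |
| 86 v 78 | 0.141 | 3 | 0.045 |
| 86 v 80 | 0.259 | 5 | 0.039 |
| 90 v 75 (planned) | 0.005 | 0 | 0.005 |

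For the first row: pooled rate 160/200 = 0.80, standard error √(0.8 × 0.2 × 0.02) = 0.0566, z = 0.10/0.0566 = 1.77. After dropping 2: 85/98 = 86.7%, pooled rate 160/198 = 0.808, standard error 0.0560, z = 0.117/0.0560 = 2.10.

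**Reading.** Selection on outcome drives the error. Unequal numbers excluded do not do so by themselves.

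**The case against.** Four things can be said for the plan.

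1. A reader might infer that exclusions are decided with arm and outcome in view. The documents do not say so. Section 12.2.1 speaks only of data review, and 8.4 calls the clinical part open without describing that review. The listed abbreviation may even show that a blind meeting was intended and not carried into the text. This stands: what can be shown is that no masking is provided for.
2. Sets are documented before hard lock, later changes are tracked, and the plan commits to ICH E9 principles and a qualified statistician. These provisions limit later changes, but none hides arm or outcome.
3. The 6.2% and 10.7% are adversarial. They remove only failures, only from Imupret, and always a fixed number. Good-faith exclusions unrelated to outcome cost almost nothing, even when unequal. This stands, and the figures must be labelled accordingly.
4. The trial calls itself exploratory, a FAS is defined beside the PPS, and no PPS test or decision is specified. This lowers the weight. It does not remove the point, because the FAS is not named as primary either, the synopsis states superiority hypotheses, and section 6.3 looks towards national guidelines.

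**Conclusion.** The gap is real: judgement-based PPS exclusions in an open trial, with no preset major deviations, no masking provision and no primary analysis set. Documenting the sets before lock does not close it.

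The size is illustrative. With 75% effective in both arms and 100 per arm, selectively removing 3 or 5 Imupret failures raises the upper-tail error from 2.5% to 6.2% or 10.7%. Exclusions unrelated to outcome leave it at about 2.5%. The counts and the test are assumptions. At the planned 90% against 75%, the result is already significant with nobody excluded, so the risk concerns null or smaller effects.

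A reader might go further and conclude that membership will be chosen by result, or that unequal exclusions must bias the comparison. The documents show neither: the first would need evidence of how the review is run, and the second fails in the enumeration above. Given the exploratory design, the point is minor to moderate: it should be corrected, but it does not by itself undermine the trial.

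**What to change.** In 12.2.1 and the SAP:

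- State that PPS membership is decided before lock at the Blind Data Review Meeting, on listings without treatment arm and efficacy results.
- Fix the list of major deviations before that review. Identify any IMP-intake criterion as applying to one arm only, and say beforehand how children who stopped the drops on the investigator's advice are classified.
- Report exclusions and their reasons by arm.
- Name the PPS as supportive of a primary analysis of all randomised patients as allocated. That analysis must be added. The current FAS requires a documented IMP application, and section 8.3 identifies the IMP as Imupret drops, so read literally it leaves out the reference arm.

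The cost is one SAP paragraph and some listing preparation. Sample size and trial conduct do not change. The drawback is that masking will be imperfect where an IMP-specific deviation reveals the arm; preset criteria and hidden outcomes still remove most of the discretion.
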